3.0 Animal Studies and Previous Human Studies

[name] and colleagues conducted a pilot study of the communication & coping intervention with 30 mothers of adolescents with type 1 diabetes, which supported the feasibility and initial efficacy of the intervention (<http://psycnet.apa.org/record/2018-09864-003>). Results from our pilot study indicated significant intervention effects on adolescents' quality of life and depressive symptoms. In addition, adolescents whose mothers received the intervention demonstrated promising improvements in glycemic control, and we found support for the effect of the intervention on mediating variables, with large effects on maternal depressive symptoms and family conflict.

4.0 Inclusion/Exclusion Criteria

List the criteria:

- mother or female caregiver to an adolescent (age 11-17)
- mother lives with adolescent at least 50% of the time
- adolescent child has been diagnosed with type 1 diabetes for at least 12 months
- mother uses Facebook regularly
- mother reports mild to moderate symptoms of depression (Patient Health Questionnaire 9 score of 5-19) OR mother reports diabetes distress (Parent/Teen Relationship Distress Subscale score of 2 or higher)
- mother and adolescent able to speak and read English
- mother and adolescent do not have a history of severe psychopathology (e.g., schizophrenia, bipolar disorder)

5.0 Enrollment/Randomization

Participants will be enrolled from the Children's Diabetes Program at Vanderbilt.

Due to the COVID-19 pandemic and social distancing requirements, a remote recruitment and enrollment protocol was established. KSP will review the diabetes clinic schedule, and participants who meet initial eligibility criteria (age, date of diagnosis) will be called the week of their clinic visit. The RA will introduce the study, and if mothers are interested, verbal consent for the screening questionnaire will be obtained. Mothers who consent will be emailed a link to the screening survey in REDCap. The RA will then email the mother to let her know if she is eligible or not. Eligible mothers will be asked to schedule a time for enrollment. At the preferred time, the mother and adolescent will be called, and the RA will provide each with a full description of the risks and benefits of the study. If they agree to participate, they will be emailed the link to sign the eConsent form in REDCap. The RA will stay on the phone while these are signed to answer any questions. Once consent/assent forms are signed, the parent and adolescent will be emailed links to complete the study surveys in REDCap. The mother will be asked to text the RA when these are completed or if they have any questions. The final enrollment will take place over the phone (demo text message and Facebook friending).

After completing all baseline data, mothers will be given instructions to "friend" the study Facebook account. Once the mother has established a connection to the study Facebook account, the mother-adolescent dyad will be randomly assigned to the intervention condition or attention control (equal numbers in each group).

Randomization will be stratified by the adolescents' treatment type (insulin pump vs. injections) and use of continuous glucose monitoring (CGM or no CGM) to remove the possibility of confounding by differences related to insulin regimen. Randomization will be determined by a computerized program created by the biostatistician on the project ([name]).

Participating mothers will be mailed a study binder and an A1C mail-in kit within 2-3 days of enrollment.

Adolescents' glycemic control will be assessed with HbA1c, which is obtained as part of regular clinical care. For adolescents who do not have an HbA1c value associated with a clinic visit (due to social distancing requirements), we will request that they use a mail-in kit. The kit includes clear instructions to provide a dried blood spot that is mailed to the lab (Coremedica). When the lab value is available, KSP will notify study participants.

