Communication and Coping Randomized Clinical Trial

[name], Department of Pediatric Endocrinology, VUMC

[name], Associate Professor
Department of Pediatrics
Vanderbilt University

Table of Contents:

Study Schema

- 1.0 Background**
- 2.0 Rationale and Specific Aims**
- 3.0 Animal Studies and Previous Human Studies**
- 4.0 Inclusion/Exclusion Criteria**
- 5.0 Enrollment/Randomization**
- 6.0 Study Procedures**
- 7.0 Risks of Investigational Agents/Devices (side effects)**
- 8.0 Reporting of Adverse Events or Unanticipated Problems involving Risk to Participants or Others**
- 9.0 Study Withdrawal/Discontinuation**
- 10.0 Statistical Considerations**
- 11.0 Privacy/Confidentiality Issues**
- 12.0 Follow-up and Record Retention**

Description of Amendments

Date	Affected Section(s)	Summary of Revisions Made	Rationale
3-1-19	Study Procedures	Addition of the Satisfaction Survey at the 3-Month Study visit. Removal of the Dad's Active Support Scale (DADS)	Added to evaluate acceptability of the intervention. Removed to reduce the burden for participants. Measure was only valid for heterosexual couples. Additional questions added to Demographic questionnaire to capture secondary caregiver information.
4-16-19		Change to wording in recruitment script to obtain verbal consent for screening survey	Added the wording: "You are free to skip questions you do not wish to answer; however, this may affect your eligibility for the study." to let the participant know that skipping questions would affect eligibility.
6-17-19	Inclusion/Exclusion Criteria	Addition of Parent Diabetes Distress Scale (Parent-DDS) as a measure of eligibility. Participant can either score 2 or higher on the Parent-DDS or have a score of 5-19 on the Patient Health Questionnaire 9 (PHQ-9) to be eligible.	In response to lower than expected enrollment, we expanded eligibility to include mothers who report clinically significant diabetes distress and who may benefit from intervention. We also expanded eligibility to include mothers who use Facebook 2-4 days a week rather than at least 5-6 days a week.
6-17-19	Enrollment/Randomization	Mother will be friended on Facebook during enrollment rather than sent an email.	Ensures that mother gets into Facebook group on the day of enrollment.

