At baseline and 6 months data collection, adolescent-mother dyads will participate in a 15-minute videotaped conversation about diabetes-related stress. To choose the topic for the video interaction, we will use the mother's highest-rated stressor on the Response to Stress Questionnaire (Connor-Smith, Compas, Wadsworth, Thomsen, & Saltzman, 2000), completed as part of the survey data collection, which lists diabetes-specific stressors. Mothers will rate the frequency of each stressor (e.g., worrying about "bad" numbers, remembering diabetes supplies) on a 4-point Likert scale ranging from 0 (never) to 3 (almost every day). Each dyad will be given a cue card with questions regarding the highest-rated stressor (e.g., What happened the last time we [had to] you remember diabetes supplies], what kind of emotions do we have when we [have to remember diabetes supplies]? How can we reduce this stress?) to guide their discussion during the videotaped interaction. This protocol has been used successfully in other studies conducted by [name], and she has trained several cohorts of raters on the Iowa Family Interaction Rating Scales to be reliable coders.

The interaction will be recorded using study iPads. Video files will be transferred from the passcoded iPad to an encrypted study computer, and then uploaded to Enterprise Storage, the secure, shared drive. Video files will only be viewed by KSP.

Mothers in the study will have 7 individual phone calls with a trained member of our research staff to discuss the information in the binders. Calls will last approximately 10-30 minutes. Mothers assigned to the Communication & Coping group will discuss content related to coping with diabetes-related stress and positive parenting strategies, following the study manual mailed to participants after randomization. The content of this manual was reviewed by a coder trained in health literacy at Vanderbilt's Effective Health Communication Core. Each session was given a Suitability Assessment of Materials (SAM) score to objectively assess the materials for clear communication and health information design (content, literacy demand, graphics, layout and typography, learning stimulation, and cultural appropriateness). Scores of 70% to 100% are considered superior material suitable for low health literacy individuals (Doak, Doak, & Root, 1996). On the SAM scale, our sessions were rated 78% to 86%, with a reading

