level of 6th-7th grade. In addition, the Patient Education Materials Assessment Tool (PEMAT) was used to assess the understandability and actionability of our intervention materials, with specific suggestions to raise these scores further (e.g., add pictures, highlight goals for each session; Shoemaker, Wolf, & Brach, 2013). On the PEMAT, the scores for individual sessions ranged from 79% to 92% (higher scores indicate that material is more understandable or actionable). All recommendations for changes were incorporated into the final versions of the manual.

Mothers assigned to the Diabetes Education group will discuss content related to diabetes management, in line with the educational materials mailed to participants after randomization. These materials were based on information available on the American Diabetes Association website (www.diabetes.org). Mothers in the Diabetes Education group will be given the option to receive the manual containing the Communication and Coping content at the 12 month visit, after the mother has completed the study. The first 5 calls will occur weekly, and the last 2 "booster" calls will occur monthly. The calls will be scheduled at a time that is convenient for study participants. These calls will be audio recorded and 20% will be randomly assessed for fidelity by an objective rater. Audio files of the intervention sessions will be stored on the same secure, shared drive and will only be accessed by trained research staff to assess fidelity or for training purposes.

Study participants will be required to "friend" the study Facebook account before they are added to the secret groups to ensure that the correct person is added. All mothers in the study will receive 1 post per day for 3 months. The posts will be on topics related to the group assignment (communication and coping or diabetes education). A moderator will view and respond to all comments made by Facebook group members. Facebook data will be extracted using programming stored on a protected server and stored in a de-identified SPSS file.

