10.0 Statistical Considerations

Baseline variables known to be associated with parenting including age, sex, income, and marital status will be compared by treatment group using the Kruskal-Wallis test (continuous variables) or Pearson's Chi-squared test (categorical variables). We will also examine if diabetes-related variables (e.g., duration of diabetes, baseline A1C) are associated with treatment group. *A priori*, we assume that our block randomization will lead to well-balanced groups so that we will not need to control for additional confounders.

Effects of the Intervention: We will estimate the effect of the intervention on each of the continuous outcomes by fitting linear mixed-effects models developed. In modeling, outcomes will be considered at their key time-points (baseline, 3 months, 6 months, and 12 months) with treatment group and the interaction of treatment with time serving as the main explanatory variables. Such a model will allow us to test for any differences between treatment and control groups over time while accounting for baseline values. While the randomized block design should minimize confounding, we will adjust for age, income, and marital status to improve precision. The results from the adjusted and unadjusted models will be compared with respect to their estimates of the treatment effects. Our interpretation will focus on describing clinically relevant treatment effects (e.g., A1C reductions of $\geq 0.5\%$, >1 additional glucose check per day, reduction from moderate to mild depressive symptoms) with corresponding confidence intervals, rather than just significance testing. We will include a random intercept to account for within-subject correlation. The error structure of the model is assumed to be compound symmetric, and the validity of this assumption will be examined by computing Akaike Information Criteria against other common structures. Subjects will be included in the analysis if they have an outcome measured at baseline and at least one outcome measured 6 or 12 months later.

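### For remotely enrolled adolescents with no clinic HbA1c, the first A1C comes from a kit mailed after randomization, and an unreturned kit drops the dyad from the A1C analysis

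*Combined protocol and SAP*

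**What the plan says.** The combined protocol and SAP deals with this in three sections.

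- **Section 5.0, order of events.** "After completing all baseline data, mothers will be given instructions to" connect with the study Facebook account. Then: "Once the mother has established a connection to the study Facebook account, the mother-adolescent dyad will be randomly assigned". The connection is made during the enrollment call: "The final enrollment will take place over the phone (demo text message and Facebook friending".
- **Section 5.0, mailing.** "Participating mothers will be mailed a study binder and an A1C mail-in kit within 2-3 days of enrollment". The section then gives routine clinical care as the source of HbA1c. The mail-in kit is requested only from adolescents who lack a value from a clinic visit.
- **Section 6.0, arm materials.** Calls in the intervention arm proceed "following the study manual mailed to participants after randomization". Calls in the education arm are "in line with the educational materials mailed to participants after randomization".
- **Section 10.0, analysis set.** "Subjects will be included in the analysis if they have an outcome measured at baseline", and they must also have at least one outcome at 6 or 12 months.

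The amendment log gives a reason for the June 2019 change to Facebook friending at enrollment: "Ensures that mother gets into Facebook group on the day of enrollment". This is supporting evidence only, but it fits randomization on the enrollment day.

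**The concern.** A baseline value should be fixed before the arm is known. If the only source is a kit that leaves the study office after assignment, in the same mailing as arm-specific content, two things follow.

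First, whether a baseline A1C exists at all depends on what the family does after allocation. The inclusion rule in section 10.0 turns that behavior into membership of the analysis set. If return differs by arm, or is related to glycemic control, the A1C comparison is no longer protected by randomization. Section 10.0 itself warns that analyzing only complete cases biases results, but its proposed check concerns missed follow-up visits, not a missing baseline.

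Second, the treatment-by-time model uses baseline as the pre-treatment reference. A sample given after daily posts have begun, and possibly after calls have begun, can already contain some treatment effect, and this would shrink the estimated difference.

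A1C is the outcome on which the enrollment target is based.

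**Working it through.** **Sequence, from sections 5.0 and 6.0**

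1. Consent, then surveys, then Facebook connection during the enrollment call.
2. Random assignment once the connection exists.
3. Binder and A1C kit mailed 2-3 days after enrollment. Section 6.0 confirms that each arm's materials follow randomization.
4. An adolescent with a clinic HbA1c from the recruitment visit has a baseline before step 2. An adolescent without one can supply a first A1C only after step 3.

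For the second group, step 3 contradicts the statement that baseline data are complete before step 2. The plan does not label the kit as a baseline kit. That is an inference: the kit is posted within days of enrollment, and the next assessment is at 3 months.

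**The plan's sample size, reproduced**

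Inputs from section 10.0: SD 1.16, correlation 0.60, difference 0.5, alpha 0.05 (taken as two-sided), power 80%. Allocation is equal (section 5.0).

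SD of a subject's mean over m measurements = 1.16 × √[(1 + (m − 1) × 0.60)/m]

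- m = 4: 1.16 × √(2.8/4) = 0.9705
- m = 3: 1.16 × √(2.2/3) = 0.9934
- m = 2: 1.16 × √(1.6/2) = 1.0375

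A two-sample t calculation with these SDs needs 122, 126 and 138 subjects. The plan's 122 and 138 reproduce exactly. Attrition: 154 × 0.85 = 130.9, which matches the planned 130. The sample-size arithmetic is sound. The margin above 122 is 130 − 122 = 8 dyads if all have four measurements, and above 126 it is 4 dyads if all have three.

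**Illustration of lost baselines**

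The documents do not give the share relying on the kit or the return rate. Assume half of the 130 rely on it (65) and 10% to 30% of kits are not returned:

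- 65 × 0.10 = 6.5 lost, N about 124
- 65 × 0.30 = 19.5 lost, N about 110

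| N | Power, 4 measures | Power, 2 measures |
|---|---|---|
| 130 | 83.0% | 77.8% |
| 124 | 81.2% | 75.9% |
| 110 | 76.3% | 70.7% |

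**Illustration of early effect in the baseline**

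Assume the effect builds linearly to 0.5% at week 12 and the sample is taken 1 to 4 weeks after randomization. The baseline then absorbs 0.5 × 1/12 = 0.04% to 0.5 × 4/12 = 0.17%. This applies to kit users only. If they are half the sample, the average is about 0.02% to 0.08%.

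**The case against.** The strongest reply is that the plan's default is a clinic HbA1c, and that remote candidates are telephoned in the week of a clinic visit, so many will have a value before allocation. This stands. A reader might infer that every remote enrollee has a post-randomization baseline, and the documents do not support that. They do provide for adolescents without a clinic value, and the amendment log records telehealth visits and recruitment through research lists, so the subgroup is unlikely to be empty. Its size is unknown. Recruitment was under way by June 2019 and the remote protocol dates from May 2020, so part of the sample is not remote at all.

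A reader might also infer that an unreturned kit removes the dyad from the trial. It does not. The inclusion rule works outcome by outcome, and the baseline surveys, including the adherence measure, are completed before randomization.

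The power figures are also open to challenge. The losses are taken from 130, which is already net of 15% attrition, and families who do not return kits may overlap with those who drop out. At N = 124 with four measures, power stays above 80%. With two measures it is below 80% before any kit is lost, so that shortfall has another cause. All this stands. Nothing in the plan says, however, that the 15% covers missing baselines, and a loss of power is not the main harm. Selection after allocation remains a problem even where power is adequate.

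Finally, the timing of the first call relative to the kit is not stated, so it cannot be claimed that kit samples follow the start of calls.

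**Conclusion.** The concern holds for remotely enrolled adolescents without a clinic-visit HbA1c. For them, the plan as written yields a first A1C after allocation, contrary to its own statement about baseline data, and makes entry to the A1C analysis depend on post-allocation behavior. This rests on reading the early kit as the source of the baseline value, which the mailing time supports but the text does not state.

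The size cannot be derived from the documents. The fall from 83.0% to 81.2% (four measures, N = 124) and the wider ranges show what assumed kit shares and return rates would do; they are not estimates for this trial. The 0.04% to 0.17% of absorbed effect is likewise conditional on an assumed linear build-up and an assumed delay, and concerns kit users alone. A reader might conclude that the trial is shown to be underpowered for this reason, or that its overall A1C effect is understated by that amount. The documents support neither conclusion.

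**What to change.** **Section 5.0.** Mail the kit at consent, separately from the binder, and ask for the sample before randomization. Do not make a returned result a condition of randomization, because that could lose families between consent and allocation. Record the date of every baseline A1C, clinic or kit, relative to randomization.

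**Section 10.0.** For A1C, remove the requirement for a baseline outcome, so that every randomized dyad with any A1C value enters the mixed model. Treat samples dated after randomization as missing baselines in the main analysis. Add a sensitivity analysis that keeps them as baseline. Where sample dates can be recovered, the same rule can be applied to dyads already enrolled.

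**Cost.** One extra mailing, one date field, a possible short delay for some families, and slightly less precision where late samples are not used as baseline.

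### The A1C model holds one pre-treatment A1C, as a first outcome with a free group term; adjusting for baseline and then for an earlier clinic A1C would gain precision, the second step by 0 to 24% of variance

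*Combined protocol and SAP*

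**What the plan says.** - **Source of A1C.** Section 5.0: adolescents' glycemic control is assessed with "HbA1c, which is obtained as part of regular clinical care". A mail-in dried-blood-spot kit is the fallback: "For adolescents who do not have an HbA1c value associated with a clinic visit", they are asked to use the kit.
- **Time since diagnosis.** Section 4.0 requires that the "adolescent child has been diagnosed with type 1 diabetes for at least 12 months".
- **Timing of approach.** Section 5.0: families who meet the initial criteria "will be called the week of their clinic visit". Also: "Participating mothers will be mailed a study binder and an A1C mail-in kit within 2-3 days of enrollment".
- **Model.** Section 10.0 lists four occasions for each outcome, the first being baseline: "outcomes will be considered at their key time-points (baseline, 3 months, 6 months, and 12 months"). The main terms are group and its interaction with time. There is a random intercept, and compound-symmetric errors are assumed and checked by AIC. Baseline A1C is therefore part of the outcome vector, and the group term leaves the two baseline means free to differ.
- **Precision covariates.** Section 10.0: "we will adjust for age, income, and marital status to improve precision". No section uses an A1C from before baseline.

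**The concern.** The plan already adjusts for covariates to gain precision, but the ones it names are demographic. An earlier reading of the outcome itself is likely to predict later A1C better. It is fixed before randomization, and for patients of the recruiting clinic it should be in the record. With a repeat correlation of only 0.60, a single baseline A1C is a noisy measure of an adolescent's usual level.

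The way baseline enters the model also matters. With a free group term, the group-by-time contrasts compare changes from baseline. Changes carry the full noise of the baseline reading, and under compound symmetry they leave an earlier A1C nothing to explain. At stake is the width of the confidence interval for the A1C effect, not its validity.

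**Working it through.** **Inputs.** All from Section 10.0 unless noted: SD 1.16; correlation of repeated A1C ρ = 0.60; target difference 0.5%; 80% power; α = 0.05 (taken as two-sided, which reproduces the figures); 130 analysed; equal allocation (Section 5.0). Not given: the correlation of a pre-enrolment A1C with later values.

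**1. The plan's own figures.** They follow from the variance factor for the mean of m equally correlated measurements, (1 + (m − 1)ρ)/m.
- m = 4: (1 + 1.8)/4 = 0.70, giving a total N of 120 by the normal formula and 122 with the t distribution.
- m = 2: (1 + 0.6)/2 = 0.80, giving 136 and 138.

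The stated 122 and 138 reproduce. They take no credit for baseline adjustment or for any earlier value.

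**2. The model as written, at one follow-up visit.** The contrast is a difference in change from baseline, with variance factor 2(1 − ρ) = 0.80. (That this equals the m = 2 factor above is a coincidence at ρ = 0.60.) The covariance of that change with an earlier A1C, in units of the outcome variance, is ρ − ρ = 0. Under compound symmetry with complete data, the earlier value therefore cannot reduce it.

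**3. Baseline as a covariate, or baseline means constrained equal.**
- One visit: 1 − ρ² = 1 − 0.36 = 0.64, which is 20% below 0.80.
- Mean of three follow-ups: (1 + 2ρ)/3 − ρ² = 0.7333 − 0.36 = 0.3733.

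**4. Adding the earlier A1C.** With two equally correlated pre-treatment values, ρ² becomes 2ρ²/(1 + ρ) = 0.72/1.6 = 0.45.
- One visit: 1 − 0.45 = 0.55.
- Mean of three: 0.7333 − 0.45 = 0.2833.

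The standard error at N = 130 is 1.16 × √(factor × 4/130). The detectable difference at 80% power is (1.96 + 0.84) × SE.

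| Constant ρ = 0.60 | Factor | SE | Detectable difference | Power for 0.5% | N for 80% power |
|---|---|---|---|---|---|
| One visit, baseline only | 0.640 | 0.163 | 0.46% | 86.7% | 110 |
| One visit, plus earlier A1C | 0.550 | 0.151 | 0.42% | 91.2% | 94 |
| Mean of three, baseline only | 0.373 | 0.124 | 0.35% | 98.0% | 64 |
| Mean of three, plus earlier A1C | 0.283 | 0.108 | 0.30% | 99.6% | 48 |

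The variance reductions from the earlier value are 1 − 0.55/0.64 = 14.1% and 1 − 0.2833/0.3733 = 24.1%.

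**5. Check by simulation.** Four mixed models were fitted to 150 simulated compound-symmetric trials of 130. The mean model SE of the 12-month contrast was:
- as written: 0.1816;
- as written, plus earlier A1C as a main effect: 0.1816;
- baseline means constrained equal: 0.1623;
- constrained, plus earlier A1C: 0.1505.

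**6. If correlation decays (assumed patterns, baseline-adjusted analysis).**
- Autoregressive of order 1: 0% gain.
- 0.60 at 3 months, falling to about 0.41 at 12 to 15 months: 0.8194 to 0.7806 at month 12 (4.7%), and 0.4194 to 0.3846 for the mean of three (8.3%).
- 0.78·exp(−0.045 × months), earlier value 3 months before baseline: 0.7934 to 0.7791 (1.8%) and 0.3996 to 0.3766 (5.8%).
- Both correlations with baseline held at 0.60, and the earlier value correlating 0.50, 0.45 or 0.36 with month 12: 4.8%, 2.0% or 0% at that visit.

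**The case against.** The strongest reply is that nothing here is broken. The sample size reproduces, Section 10.0 already names covariates for precision, and the choice among them is the analyst's. It stands that this is not a defect.

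The second reply is that the obvious remedy fails: adding an earlier A1C to the planned model leaves the change-from-baseline contrasts exactly where they were. That also stands, and it is why the handling of baseline must change first. At a single visit that step gains more (20%) than the extra value does even at constant correlation (14%).

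Third, the upper end of the gain needs a correlation that does not fade over time. The documents offer one pilot figure of 0.60 and nothing on pre-enrolment values. This stands too. Constant correlation is the plan's own working assumption, but one it intends to check.

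Three stronger readings are tempting and not supported:
- *That every moderation and mediation analysis gains.* No such calculation is available. An earlier A1C is not aimed at the path from treatment to mediator, and the plan already states power above 99% for mediation through family conflict.
- *That adolescents with a missing baseline A1C are recovered.* Section 10.0 admits a subject only with a baseline outcome and a 6- or 12-month outcome. A covariate does not change that rule.
- *That the value is free and always there.* Section 5.0 names one clinic, but the June and July 2021 entries in the amendment table add wider recruitment channels, so some records may lie elsewhere. The kit exists because clinic values were missing under social distancing, and a look-back over that period may have gaps. Mixed clinic and kit assays could also lower the correlation. Whether consent covers earlier values cannot be judged from the text available.

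**Conclusion.** The point holds as an optional, low-cost improvement. The A1C analysis uses one pre-treatment value, in the position where it helps least. Under the plan's ρ of 0.60, adjusting for baseline lowers the single-visit variance factor from 0.80 to 0.64. An earlier clinic A1C then lowers it by a further 14%, or by 24% for the three-visit mean, if correlation is constant. If correlation decays, the further gain is about 0 to 8%. The full range for the second step is therefore 0 to 24%, conditional on the first step, complete data and SD 1.16 with 130 analysed. A reader might infer that the trial is underpowered or its analysis invalid without this; the documents support neither.

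One consideration in favour does not depend on the correlation. Because kits are mailed after enrollment, a kit-based baseline A1C could come back after assignment, whereas an earlier clinic value is certainly pre-randomization.

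**What to change.** Pre-specify for the A1C models in Section 10.0:
1. Take baseline A1C out of the outcome vector and enter it as a covariate, with 3, 6 and 12 months as outcomes; or keep it as an outcome and constrain the two baseline group means to be equal.
2. Add as a second covariate the most recent clinic A1C dated before the baseline A1C, within a stated look-back window (for example 6 months). Do not define it as the last value before enrollment: families are approached around a clinic visit, so that value may be the baseline itself.
3. Where no earlier value exists, fill it by single imputation from baseline A1C, without using arm or follow-up data, so that no dyad is lost.
4. Record the date and source (clinic or kit) of both values.

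If dyads without a baseline A1C are to be kept, the inclusion rule in Section 10.0 must be changed separately.

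The cost is one chart abstraction per adolescent and a check that consent covers it. The earlier values will have varying dates, some will be missing or held elsewhere, and the gain may prove small. Step 1 needs no new data and is worth making even if step 2 is declined.
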